5.3.2 Anthropometric assessments

BRTC staff will measure the participants' height, weight, and waist circumference at baseline and 4th month. Height will be measured by having the participant stand evenly without shoes on a flat surface at a right angle to the movable vertical board or cap that is pulled down to lightly touch the most superior point of the head. Weight will be measured using either a standard beam scale or an electronic digital scale. The scale should be on a level floor, and participants should be gowned or wearing light clothing and no shoes. Waist circumference will be measured with the participant standing relaxed with hands hanging at her sides on the exhale. The tension-controlled measurement tape will be placed directly on the skin, horizontally around the narrowest part of the torso. If unable to locate the narrowest part of the waist, the participant will be measured 2-3 inches above the navel. The hip circumference will be measured with the participant standing relaxed with hands hanging at her sides on the exhale. The tension-controlled measurement tape will be placed directly on the skin or over the underwear, horizontally around the widest part of the hip/buttocks area.

The participant will undergo a whole body DEXA to measure body composition. The DEXA, routinely used to determine bone mineral density, has gained support in research application for assessing fat and lean body mass in whole body and in specific body regions [23, 24, 25]. Data from each scan will be as follows: percent body fat and % lean tissue, fat and lean mass for total body region as well as defined body zones (trunk, leg, and arms) expressed in grams.

5.4 Randomization / Visit 3

Participants, who are eligible based on results of the biopsy from Visit 2, will be called to schedule their third visit for randomization.

This study will use a 2 x 2 randomized design with all 100 subjects being randomized: 25 will receive both lifestyle intervention and metformin, 25 will receive the lifestyle intervention plus metformin placebo, 25 will receive metformin only, and 25 will receive metformin placebo but no lifestyle intervention. The participants randomized to the lifestyle change portion of the study will also have their first intervention session schedule for the same day as well. Treatments will last 4 months.

At Randomization / Visit 3, the participant will be:

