7.0 Data Monitoring Plan

Participants will be randomized to one of the four arms: metformin, placebo, and metformin / placebo and lifestyle intervention using the Department of Biostatistics Clinical Trial Conduct Website (CTC website). Participants who do not meet these criteria will be considered nonevaluable, removed from study and will not be counted toward the actual accrual goal. We plan to accrue 100 evaluable participants.

We will use a form of adaptive randomization called minimization, which is similar to stratification in that participant characteristics are used to assign them to the treatment conditions [75, 76]. Minimization results in better group balance with respect to participant characteristics. In minimization, before a participant is assigned to a treatment group, the total numbers of participants in each group with similar covariate characteristics are totaled. The totals are based on the marginal sums of the covariates so that each covariate is considered separately. The treatment assignment of a participant is determined based on which group would provide the best overall balance with respect to those covariates. Covariates that will be used in randomization of participants in this study are BMI, age, and whether the participant meets current guidelines for exercise recommended by the Physical Activity Guidelines for Americans. These guidelines recommend that adults engage in moderate physical activity at least 150 minutes per week or in vigorous activity 75 minutes per week [77]. The baseline level of activity for each participant will be measured when they complete the Godin questionnaire, which is part of their survey packet, which will be completed before their Screening Visit 2 appointment. The Research Dietitian/Research Coordinator will determine if the participant is currently meeting these recommendations and provide

this data to the Research Nurse for randomization.

Randomization will be performed by the research nurse using the website created by the Department of Biostatistics. The research nurse will then inform the pharmacist of randomization group (A, B, C, or D) for study drug administration. The Research Dietitian/Research Coordinator who is in charge of administering the lifestyle intervention will be given access to the randomization website and informed of lifestyle intervention randomization code to determine whether the participant has been randomized to the lifestyle intervention.

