9.0 Statistical Considerations

This is a partially blinded, randomized study to evaluate the effects of intervention upon Ki-67 and other biomarkers. Participants and researchers will be blinded with regard to assignment of study drug (placebo vs. metformin) but they will not be blinded with regard to assignment of lifestyle intervention. We will use a form of adaptive randomization called minimization, which is similar to stratification in that participant characteristics are used to assign them to the treatment conditions to achieve better group balance. Groups will be balanced with regard to age (50-65 years), BMI (Class I and II: 30.0-39.9 and Class III or greater: ≥ 40), and whether they meet current exercise guidelines as recommended by the Physical Activity Guidelines for Americans.

The primary objective of this study is to evaluate the effect of intervention (metformin and/or lifestyle intervention) on Ki-67. Secondary endpoints include examination of intervention on:

- (a) genes relevant to estrogen dependent endometrial proliferation, hyperplasia and cancer using Q-PCR (PCNA, sFRP4, RALDH2, IGF-1R, survivin, and EIG121),
- (b) biomarkers specific to the effect of metformin treatment (phospho-AMPKa, phospho-ACC, phospho-mTOR and phospho-S6 ribosomal protein).

Additionally, we will examine changes in serum levels of estradiol, estrone, testosterone, DHEA-S, sex hormone binding globulin (SHBG), adiponectin, glucose,

HbA1c, insulin and insulin-like growth factor-1 (IGF-1) and all biobehavioral outcomes, such as changes in body composition, physical activity, quality of life (QoL), diet, etc.

We will analyze differences in Ki-67 and other outcomes using 2x2 ANOVA models. If lifestyle intervention is found to affect change in Ki-67 expression or other outcomes, we will use the methods described by Baron and Kenney [78] to determine whether these changes were mediated by weight loss, body composition changes, physical activity changes, and dietary changes. Differences between arms with regard to adverse events and other toxicities will be examined using Fisher's exact tests. Changes from baseline lab values will be examined 2x2 ANOVA models.

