A study of Ki-67 change in participants at high risk for endometrial cancer (Lynch patients) indicated we could expect a mean decrease in Ki-67 of 3.5 (after log-transformation) in the Metformin alone group with a standard deviation of 0.8. For the purposes of estimating power, we assumed that the lifestyle intervention alone group would have the same mean and standard deviation decrease, but we halved mean decrease for our calculations to take into account the non-compliance we might observe in this group. Finally, we estimated power for a moderate interaction effect – half of the metformin intervention effect in addition to the additive effect of metformin and lifestyle intervention. Specifically, we calculated power assuming that the mean decreases in the control arm, metformin alone arm, lifestyle intervention alone arm and metformin plus lifestyle intervention arm were 0, 3.5, 1.75 and 7, respectively. Using a 2-sided test with 5% statistical significance, we will have over 95% power to detect these differences when the common standard deviation is 0.8. Additionally, we will still have adequate power to detect much smaller differences. For example, we will have 80% power to detect a lifestyle alone main effect of 0.3 and still have over 95% power to detect a metformin main effect and an interaction effect of 0.6 and 1.2, respectively, when the common standard deviation is 0.8. Power was calculated using PASS 2005 (copyright

© 2005, Jerry Hintze).

All testing will be 2-sided with 5% statistical significance. The primary efficacy analysis will be intent-to-treat. Patients who discontinue early from the study will be included in the analysis as not having a change from baseline values. Additionally, we will use the methods described by Benjamini and Hochberg [51] to control the false discovery rate in the secondary efficacy analyses.

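### Causal-steps mediation, run only after a significant lifestyle effect, gives no indirect-effect estimate and loses real mediation when that effect is modest; how discontinuers enter it is not stated

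*Combined protocol and SAP*

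**What the plan says.** All statements are in Section 9.0 of the combined protocol and SAP unless noted.

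- Outcomes are compared with 2x2 ANOVA models. If lifestyle is found to affect Ki-67 or another outcome, "we will use the methods described by Baron and Kenney [78] to determine whether these changes were mediated by weight loss", and likewise by changes in body composition, activity and diet.
- "All testing will be 2-sided with 5% statistical significance". I therefore read a lifestyle effect being found as a significant test at that level.
- Directly after the sentence making the primary efficacy analysis intent-to-treat comes the rule for dropouts: "Patients who discontinue early from the study will be included in the analysis as not having a change from baseline values". It names no variable and does not mention the mediation models.
- On size, Section 7.0 says "We plan to accrue 100 evaluable participants", and Section 5.4 splits them 25 per arm, so the lifestyle margin is 50 v 50.
- The document gives no indirect-effect estimate or interval, no mediation power, no dropout rate and no SD for any mediator.

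**The concern.** Causal steps declare mediation from a chain of significance tests: lifestyle on outcome, lifestyle on mediator, mediator on outcome given arm, and a lifestyle coefficient that shrinks. The answer is yes or no, without a size. The first link, which the plan also writes in as a precondition, is often the weakest. The lifestyle-to-weight path and the weight-to-Ki-67 path can both be clear while their product, the total effect, misses 5%. A direct test of the indirect effect does not need that link.

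The second issue concerns women who leave early. If they are set to zero on both mediator and outcome, a cluster at (0,0) appears inside the lifestyle arms. That cluster alone makes mediator and outcome correlate within arm, and the models would read the correlation as mediation.

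At stake is the trial's explanation of how the lifestyle programme works. The primary Ki-67 test and the sample size are not affected.

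**Working it through.** **1. The plan's own power figure, which is the power of the gate.** The smaller example says "we will have 80% power to detect a lifestyle alone main effect of 0.3", with 0.6 and 1.2 for the other two effects. Read 0, 0.6, 0.3 and 1.2 as means for control, metformin, lifestyle and both, in the same ratio as the planning means.

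- Marginal lifestyle effect = [(0.3 - 0) + (1.2 - 0.6)]/2 = 0.45. In SD units, 0.45/0.8 = 0.56.
- Standard error = 0.8 x sqrt(2/50) = 0.16. Power = Phi(0.45/0.16 - 1.96) = Phi(0.85) = 80%, so the stated figure reproduces. Taking 0.3 itself as the marginal effect gives only 47%.
- For the planning means ("lifestyle intervention alone arm and metformin plus lifestyle intervention arm were 0, 3.5, 1.75 and 7, respectively"): [1.75 + (7 - 3.5)]/2 = 2.625, or 3.28 SD, and 2.625/0.16 = 16.4. The gate is passed almost surely.

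**2. What the gate costs.** Assumed inputs: unit residual SDs, lifestyle shifts the mediator by *a*, mediator slope *b*, direct effect *c*, no dropout. The total effect is *ab* + *c*, the outcome SD is sqrt(1 + *b*²), and one SD of residual gives a standard error of sqrt(2/50) = 0.2.

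- Gate power = Phi[(*ab* + *c*)/(0.2 sqrt(1 + *b*²)) - 1.96]
- Power of both paths = Phi(*a*/0.2 - 1.96) x Phi(*b* sqrt(97) - 1.96)

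For *a* = 0.8, *b* = 0.4, *c* = 0, the gate is Phi(0.32/0.2154 - 1.96) = 32%, and the paths are Phi(2.04) x Phi(1.98) = 0.979 x 0.976 = 96%. The last two columns are simulated, 50 v 50, with ranges over independent runs.

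| *a*, *b*, *c* | Total effect | Gate (formula) | Both paths (formula) | Gated causal steps | Interval for *ab* |
|---|---|---|---|---|---|
| 0.6, 0.4, 0 | 0.24 | 20% | 83% | 17-18% | 81-82% |
| 0.8, 0.4, 0 | 0.32 | 32% | 96% | 28-33% | 95% |
| 0.8, 0.3, 0.15 | 0.39 | 46% | 82% | 34-37% | 79-81% |
| 0.8, 0.4, 0.24 | 0.56 | 74% | 96% | 68-71% | 95% |
| 0.8, 0.4, 1.0 | 1.32 | about 100% | 96% | 95% | 95% |

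The loss is almost entirely the gate. It is 74% rather than 80% in the fourth row because the residual SD is 1 given the mediator, so the outcome SD is 1.077.

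A second simulation used the plan's smaller-effect means, its 7% weight-loss goal and an assumed SD of 5 points for weight change. With 25, 50, 75 and 100% of the effect mediated, gated power was 14, 39, 68 and 80%, and ungated power 17, 50, 87 and 99%. At the planning means, gated power was 65% at 10% mediated and 100% at 25% or more.

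**3. What joint zero-coding would do.** Assume no true mediation (*b* = 0), a lifestyle effect of D SD on the outcome, and a fraction *d* leaving at random, equally in both groups.

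- Within the lifestyle group, joint zero-coding creates a covariance of *d*(1 - *d*)*a*D. Pooling over both groups, the false slope is *da*D/(2 + *da*²).
- Pooled within-group variances are (1 - *d*)(1 + *da*²/2) for the mediator and (1 - *d*)(1 + *d*D²/2) for the outcome.

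With *d* = 0.2, *a* = 0.8, D = 1.5: slope = 0.24/2.128 = 0.113; variances 0.851 and 0.98; residual variance 0.98 - 0.113² x 0.851 = 0.969; standard error = sqrt[0.969/(97 x 0.851)] = 0.108; rejection = Phi(1.04 - 1.96) = 18%.

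| *a*, D (20% dropout) | Formula | Simulated, gated causal steps |
|---|---|---|
| 0.8, up to 0.56 | about 5% at 0.56 | 0.2-6% |
| 0.8, 1.5 | 18% | 19% |
| 0.8, 2.2 (= 1.75/0.8) | 28% | 29% |
| 1.4 (= 7/5), 2.2 | 65% | 62% |

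With zero-coding of the outcome only, or completers only, the rate was about 5% or less. Carrying the four planning means in full, at 20% dropout, gave 15, 57 and 87% for weight effects of 3, 5 and 7 points (SD 5), so the size depends strongly on the assumptions.

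**The case against.** **A reader might infer that the mediation question would usually go unanswered.** The documents do not support that. The low detection rates belong to total effects of 0.24-0.39 SD. The plan's smaller example is 0.56 SD and its planning effects are far larger, and at those nothing is lost once a quarter of the effect is mediated. One can add that, with no detected lifestyle effect, the plan's question about what mediated the change does not arise. The first part stands and limits the point to modest effects. The second stands only in part: an indirect effect can be estimated, with its uncertainty, whether or not the total reaches 5%.

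**A reader might infer that the plan builds in false mediation.** It does not say so. The zero-change rule sits beside the primary efficacy analysis, and nothing applies it to the mediators. Section 6.4 also records weight at each monthly visit, so many women who stop early would have an observed weight. What remains is ambiguity: Section 1.2 lists body composition, diet and activity as endpoints, and the rule names no variable, so an analyst could apply it to them.

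**The two problems hardly coincide.** Where the gate costs power it also holds false mediation down; where false mediation would be high, power is not low. This stands.

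**Dropping the gate everywhere invites multiplicity.** Ki-67, 6 genes, 4 phosphoproteins and 10 serum markers make 21 outcomes, and 21 x 4 mediator groups = 84 indirect effects. A completers analysis can also be biased if leaving is related to weight loss. Both stand and shape the fix.

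**Mediation is in no objective or endpoint.** True, so this is a low-cost improvement and does not threaten the primary result.

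**Conclusion.** The point holds in limited form. The gated causal-steps plan yields no indirect-effect estimate or interval. It also loses real mediation when the lifestyle effect is modest: about 68% against 95% at 0.56 SD, and 18-37% against 79-95% at 0.24-0.39 SD. There is no loss at the planning effects. These figures rest on assumed mediator paths, and the 0.56 rests on the reading that reproduces the plan's 80%.

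The false-mediation part is conditional. Only if the zero-change rule were carried over to mediator and outcome together would the error rise, to about 19-62% at 20% dropout with lifestyle effects of 1.5-2.2 SD, against about 5% otherwise. Dropout, its randomness and the mediator SDs are assumptions, because the documents give none. What can be said of the plan itself is that its handling of discontinuers in the mediation models is unspecified.

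**What to change.** In Section 9.0:

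- Estimate the indirect effect as a product of coefficients with a bootstrap or Monte Carlo 95% interval, adjusted for baseline values and metformin assignment.
- For Ki-67, report it whether or not the total lifestyle effect is significant. For other outcomes, name a limited set or apply the Benjamini-Hochberg control already planned for the secondary analyses.
- State that mediator and outcome are not jointly set to zero for women who discontinue. Use observed values with multiple imputation, and completers as a sensitivity analysis.
- Label the analysis exploratory, because mediator and outcome are both measured at the month-4 evaluation and their order in time cannot be shown.

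The cost is a paragraph of SAP wording, slightly more analysis work and more exploratory estimates to report. No visits, samples or participants are added.

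### The power figures for smaller effects cannot all be right: read as arm means, the interaction has about 15% power (stated over 95%); read as contrasts, lifestyle has about 46% (stated 80%)

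*Combined protocol and SAP*

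**What the plan says.** Section 9.0 of the combined protocol and SAP bases power on the change in log-transformed Ki-67.

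- **Headline case.** Mean decreases in the control, metformin, lifestyle and combination arms "were 0, 3.5, 1.75 and 7, respectively", with SD 0.8 and power above 95%. The interaction built into these means is "half of the metformin intervention effect in addition to the additive effect of metformin and lifestyle intervention".
- **Smaller effects.** The section then says power remains adequate for much smaller differences. Its one example is "80% power to detect a lifestyle alone main effect of 0.3 and still have over 95% power to detect a metformin main effect". The metformin figure is 0.6, and the same power is claimed for an interaction of 1.2, again at SD 0.8.
- **Analysis.** "We will analyze differences in Ki-67 and other outcomes using 2x2 ANOVA models". "All testing will be 2-sided with 5% statistical significance".
- **Size.** Section 5.4 allocates 100 women equally to four arms ("25 will receive both lifestyle intervention and metformin", and 25 in each of the others).
- **Discontinuation.** "Patients who discontinue early from the study will be included in the analysis as not having a change from baseline values".

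**The concern.** The example uses the terms main effect and interaction effect, which in a 2x2 ANOVA are contrasts. Yet 0.6, 0.3 and 1.2 stand in the same 2 : 1 : 4 ratio as the headline arm means 3.5, 1.75 and 7. A main effect of 0.3 is also small for this design: its standard error is 0.16, so it lies fewer than two standard errors from zero, and 80% power is not possible. One of the three powers therefore looked wrong whichever way the numbers are read.

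The example matters because the headline metformin effect is very large (3.5 / 0.8 = 4.4 SD). The example is the plan's only numerical support for power if that assumption fails. Section 1.1.1 sets the primary objective as the independent effects of the two interventions, so whether they interact bears on how the main effects are read. Someone who believes a modest interaction is tested with over 95% power could take a non-significant result as good evidence that the effects simply add. On the literal reading, a lifestyle main effect of 0.3 would be missed more often than found.

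**Working it through.** **Inputs.** n = 25 per arm (section 5.4); SD 0.8, two-sided 5%, 2x2 ANOVA (section 9.0). Error df = 100 − 4 = 96.

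**Formulas.** With arm means C (control), M (metformin), L (lifestyle) and B (both):

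- Metformin main effect = [(M − C) + (B − L)] / 2
- Lifestyle main effect = [(L − C) + (B − M)] / 2
- Interaction = B − M − L + C
- SE of a main effect = 0.8 × √(4/100) = 0.16
- SE of the interaction = 0.8 × √(4/25) = 0.32
- Power is from the noncentral F with 1 and 96 df, noncentrality λ = (effect / SE)², critical value 3.94.

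**Headline case, 0 / 3.5 / 1.75 / 7.** Metformin 4.375, lifestyle 2.625, interaction 7 − 3.5 − 1.75 = 1.75. All three powers exceed 99.9%, so the claim of over 95% reproduces. The interaction of 1.75 is half of 3.5, as the plan defines it.

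**Smaller effects, the two natural readings.**

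| | Stated | Read as contrasts | Read as arm means 0 / 0.6 / 0.3 / 1.2 |
|---|---|---|---|
| Lifestyle | 80% | 0.3: λ = 3.52, **45.9%** | (0.3 + 0.6)/2 = 0.45: λ = 7.91, 79.5% |
| Metformin | over 95% | 0.6: λ = 14.06, 96.0% | (0.6 + 0.9)/2 = 0.75: λ = 21.97, 99.6% |
| Interaction | over 95% | 1.2: λ = 14.06, 96.0% | 1.2 − 0.6 − 0.3 = 0.3: λ = 0.88, **15.3%** |

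Each reading returns two of the three stated powers and misses the third by a wide margin.

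**Likely origin.** Apply the plan's own definition of the interaction to a metformin effect of 0.6. The excess over additivity is 0.3, and the combination-arm mean is 0.6 + 0.3 + 0.3 = 1.2. So 1.2 appears to be the combination-arm mean, reported as if it were the interaction.

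**Other readings tried.**

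- Simple effects of 0.3 and 0.6 with an interaction contrast of 1.2 (arm means 0 / 0.6 / 0.3 / 2.1): lifestyle and metformin over 99.9%, interaction 96.0%. No shortfall, but lifestyle is not 80%.
- Effect-coded (±) parameters: lifestyle 96.0%, the other two over 99.9%. Again lifestyle is not 80%.
- Arm means for the main effects, with 1.2 taken as combination arm versus control (SE = 0.8 × √(2/25) = 0.226): 99.9%. This fits all three figures, but that comparison is not an interaction.

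**What the design can detect.** At 80% power: a main effect of 0.453 or an interaction of 0.906. For scale only, 80% power for a main effect of 0.3 needs 57 per arm (228 in total). An interaction of 0.3 needs 224 per arm (896) for 80% and 371 per arm (1,484) for 95%.

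**Early discontinuers counted as zero change.** The documents give no rate, so 10% and 20% in every arm are assumptions. Simulation of 40,000 trials with arm means 0 / 0.6 / 0.3 / 1.2:

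| Discontinued | Metformin | Lifestyle | Interaction |
|---|---|---|---|
| 0% (exact) | 99.6% | 79.5% | 15.3% |
| 10% | 99.0% | 72.3% | 13.7% |
| 20% | 97.5% | 64.3% | 12.3% |

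**The case against.** The sentence is a secondary illustration. The sample size rests on the headline scenario, which reproduces, and no test or decision rule uses the smaller figures. On the likelier reading both main-effect powers are as stated, and those are the comparisons closest to the primary objective. The 46% then describes a case the authors probably never computed. Nothing in section 9.0 says that a non-significant interaction will be read as additivity or used to simplify the model.

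Most of this stands, and it limits the scope: the design case and the planned analysis are not in question, the harm lies in how the result might be read, and the origin of the error is inferred. It does not rescue the sentence. The plan chose to state power for an interaction that its 2x2 ANOVA will test. Differences of 15% against over 95%, or 46% against 80%, are not rounding, and nothing elsewhere in the documents reconciles them.

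**Conclusion.** The concern holds. Neither natural reading of 0.3, 0.6 and 1.2 yields the three stated powers. All three fit together only if definitions are mixed, as when 1.2 is taken as the combination arm against control. On the likelier, arm-mean reading, the one error is the interaction: 15.3% power where over 95% is claimed. On the literal, contrast reading, the one error is lifestyle: 45.9% where 80% is claimed.

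The inconsistency is certain given the plan's own inputs. Which figure is wrong is not certain, because the power software output is not in the documents. The powers assume 25 analysed per arm, a common SD of 0.8 and no early discontinuers; discontinuers counted as zero change would lower them. The headline power claim is unaffected.

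**What to change.** Check the original power run to confirm what was entered. Then replace the example in section 9.0 with text to this effect:

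> With 25 per arm and an SD of 0.8 on the log scale, there is 80% power for a main effect of about 0.45 and for an interaction contrast (difference of differences) of about 0.91. For arm means of 0 (control), 0.6 (metformin), 0.3 (lifestyle) and 1.2 (both), power is over 99% for metformin, about 80% for lifestyle and about 15% for the interaction. These figures assume no dilution from early discontinuers counted as zero change. A non-significant interaction at effects of this size is not evidence of no interaction.

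If the run shows that other arm means were intended, state those and give the power of each contrast under that one definition.

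The cost is protocol wording only. Sample size, conduct and analysis do not change; the one downside is a less favourable stated power.
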